3.2.2.5. Safety

Subjects participating in the substudy will be evaluated for safety endpoints in a separate evaluation after Day 85 re vaccination/attenuated challenge.

- Maximum daily severity during the 7 days following study vaccination (by treatment group).
- Incidence by toxicity grade during the 7 days following study vaccination (by treatment group).
- Mean response (for any measurements) and duration during the 7 days following study vaccination (by treatment group).
- All AEs through 28 days following study vaccination by severity and relationship to study vaccination (by treatment group).

- All MAAEs through 84 days following study vaccination by severity and relationship to study vaccination, and by time since study vaccination (by treatment group).
- All AESIs and SAEs through Day 169/EOS by severity and relationship to study vaccination, and by time since study vaccination (by treatment group).
- Incidence of SARS-CoV-2 infections or AESIs associated with COVID-19 disease by severity, and by time since study vaccination (by treatment group).
- *B. pertussis* clearance following study vaccination (subset of subjects at varying time points through Day 85).

3.2.3. Exploratory Endpoints

3.2.3.1. Mucosal Secretory Immunogenicity (Optional Substudy Only)

Note that S-IgA objectives and endpoints for the overall study (as noted above) will also be analyzed for the optional substudy and will be considered exploratory.

- Induction of mucosal S-IgA at Day 29 or 85 (tested independently) compared by protection against colonization (Colonizers/Non-colonizers) by treatment group (BPZE1, BPZE1 + Boostrix, BPZE1 and BPZE1 + Boostrix, Boostrix control).
- Induction of mucosal S-IgA (WCE, FHA, PRN and any additional anti-pertussis mucosal antibodies identified during assay development) at Day 113 compared with Day 85 following BPZE1 attenuated challenge by treatment group (BPZE1, BPZE1 + Boostrix).
- Induction of mucosal S-IgA at Days 113 and 169/EOS (tested independently) in subjects who participated in the substudy compared with subjects who did not participate in the substudy by treatment group.

3.2.3.2. Serum Immunogenicity (Optional Substudy Only)

Serum immunogenicity (IgA and IgG) (optional substudy only): WCE, PT, FHA, PRN, and any additional anti-pertussis antibodies identified during assay development using GMT and GMFR unless otherwise stated.

- BPZE1, BPZE1 + Boostrix, and Boostrix induction of serum immunity (IgA, IgG) at Day 113 compared with baseline (by treatment group).
- BPZE1, BPZE1 + Boostrix, and Boostrix induction of serum immunity (IgA, IgG) at Day 113 compared with Day 85 (by treatment group).
- BPZE1, BPZE1 + Boostrix, and Boostrix induction of serum immunity (IgA, IgG) at Days 113 and 169/EOS in subjects who participated in the substudy compared with subjects who did not participate in the substudy (tested independently by treatment group and day).
- BPZE1, BPZE1 + Boostrix, BPZE1 and BPZE1 + Boostrix, Boostrix induction of serum immunity (IgA, IgG) at Day 29 or Day 85 (tested independently) compared by protection against colonization (Colonizers/Non-colonizers) (tested independently by treatment group and overall).
- Proportion of subjects with $\geq 50\%$ killing (or equivalent) for functional antibody response at Day 113 compared to baseline and Day 29 (tested independently by treatment group and day).

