2.3.2. Serum Immunogenicity (Optional Substudy Only)

- To measure BPZE1 induction of serum immunity at Day 113; and to assess if induction of a boost response (relative to Day 85 response) is observed for those subjects with prior BPZE1 vaccination (BPZE1, BPZE1 + Boostrix).

- To assess if Day 113 response and longer-term immune durability through Day 169/EOS is altered with re-vaccination/attenuated challenge when compared to those subjects who did not participate in the substudy, relative to each randomized treatment group (BPZE1, BPZE1 + Boostrix, Boostrix).
- To assess if serum immunity of individual and combinations of pertussis antibodies (eg, WCE, PT, FHA, PRN, and other known anti-pertussis antibodies) at Day 29 or 85 is relational to protection against colonization by treatment group and overall (BPZE1, BPZE1 + Boostrix, Boostrix).
- To assess functional antibody response by treatment group at Day 113 compared to baseline and Day 29, as measured by an appropriate assay for bactericidal activity.

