There is an optional open-label substudy in which enrolled subjects may elect to participate at any time from the day of enrolment through Day 85. A separate signed ICF (and separate assent when necessary) will be obtained prior to participation in the substudy. Subjects will be excluded from participating in the substudy if they meet additional exclusion criteria listed in Protocol Section 4.1.2.1. Temporary vaccination holding criteria are to be followed for the Day 85 vaccination.

Up to 120 enrolled subjects may participate in the substudy. The duration of the entire study will not change; however, additional visits/procedures starting on Day 85 will include the following:

- 3 additional visits (Days 92, 99, and 113)
- 1 additional intranasal vaccination (Day 85)
- Up to 3 additional nasal samples, including 2 of those needed for midturbinate/nasopharyngeal sample collection (Days 92 and 99) and 1 needed for leukosorb (Day 113). Subjects will contribute to all Day 85 sampling (systemic and nasal).
- Up to 2 additional blood samples (Days 85, if not already assigned to provide, and 113, including blood for cellular-mediated and systemic immunity responses)
- 1 additional subject diary (subjects to record maximum daily reactogenicity [nasal/respiratory, systemic] in a subject diary for 7 consecutive days starting the day following study vaccination)
- 1 additional test for SARS-CoV-2 within 72 hours prior to Day 85 vaccination.

All subjects participating in the open-label substudy will receive an intranasal re-vaccination/attenuated challenge with BPZE1 on Day 85. Subjects may have the planned re-vaccination/attenuated challenge deferred to a later date (up to 20 days) if pre-defined temporary exclusion criteria in Protocol Section 4.1.2.1 are met or for other personal reasons (eg, holiday, school schedule). Subjects will be monitored for at least 30 minutes after re-vaccination/attenuated challenge, with a post-vaccination evaluation for reactogenicity (nasal/respiratory, and systemic) completed prior to release from clinical observation.

Subjects will receive a subject diary on Day 85. All subjects (with assistance when needed) will record maximum daily reactogenicity in a subject diary for 7 consecutive days starting the day following re-vaccination/attenuated challenge (retrospective of the highest value in the previous 24 hours).

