Immunogenicity endpoints (seroconversion, GMT/GMC/GMR, and GMFR) will be summarized by baseline PRN negative and PRN positive status, by quantiles of each anti-pertussis antibody (WCE, PT, FHA, PRN, and any additional anti-pertussis antibodies) and by antibody type (eg, S-IgA, IgA, and IgG separately), by the 2 age groups (6 to 10 years and 11 to 17 years, inclusive) and across age groups. An additional age group of 10 to 17 years will be added for some analyses to be able to support a rationale for immunobridging to adults. A forest plot will be generated for subgroups.

The substudy analysis will assess immunogenicity endpoints at baseline and Days 85 and 113 (independently for substudy subjects) and relative to colonization status (colonized/non colonized) at either or both Day 92 and/or 99 following re-vaccination/attenuated challenge at Day 85.

All statistical tests will be 2 sided at 0.05 significance level.

If a substantial number of subjects receive a COVID-19 vaccine that is under an emergency use authorization only, then safety analysis may also assess any AEs that may be confounded by such concomitant vaccine administration during the study.

All data collected will be listed in data listings.

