8.4.2. Analysis of Mucosal Secretory Immunogenicity Endpoints

BPZE1, BPZE1 + Boostrix, BPZE1 and BPZE1 + Boostrix, and Boostrix control induction of mucosal S-IgA at Days 29 and 85 will be summarized by protection against colonization (Colonizers/Non-colonizers) and by treatment group and by timepoint. Separate two-sample t-tests will be used to compare the natural log-transformed GMRs at Days 29 and 85 between Colonizers and Non-colonizers by treatment group and by timepoint.

To test the hypothesis that BPZE1 and BPZE1 + Boostrix can induce mucosal S-IgA at Day 113 compared with Day 85, separate paired t-tests will be used to compare the natural log-transformed GMCs/GMRs at Day 113 with the natural log-transformed GMCs/GMRs at Day 85 within each treatment group. The corresponding 95% CIs will be calculated on the natural log scale, then both lower and upper limits will be exponentiated to get the 95% CIs on the original scale.

BPZE1, BPZE1 + Boostrix, or Boostrix control induction of mucosal S-IgA at Day 113 and Day 169/EOS will be summarized by participation in the substudy (Yes/No) and by treatment group and by timepoint. Separate ANCOVA models that include baseline S-IgA and an indicator of participation in the substudy (Yes/No) as covariates will be used to compare between subjects who participated in the substudy and subjects who did not participate in the substudy, by treatment group and by timepoint.

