8.4.3. Analysis of Serum Immunogenicity Endpoints

To test the hypothesis that BPZE1 induction of serum immunity (IgA, IgG) at Day 113 compared with baseline, or Day 113 compared with Day 85, separate paired t-tests will be used to compare the natural log-transformed GMC at Day 113 with the natural log-transformed GMC at either baseline or Day 85 within each treatment group (BPZE1, BPZE1 + Boostrix, Boostrix). The corresponding 95% CIs will be calculated on the natural log scale, then both lower and upper limits will be exponentiated to get the 95% CIs on the original scale.

BPZE1, BPZE1 + Boostrix, and Boostrix induction of serum immunity (IgA, IgG) at Day 113 and Day 169/EOS will be summarized by participation in the substudy (Yes/No) and by treatment group and by timepoint. Separate two sample t-tests will be used to compare the natural log-transformed GMCs at Day 113 and Day 169/EOS between subjects who participated in the substudy and subjects who did not participate in the substudy (Day 169/EOS only), by treatment group and by timepoint.

BPZE1, BPZE1+Boostrix, BPZE1 and BPZE1+Boostrix, Boostrix control induction of serum immunity (IgA, IgG) at Days 29 and 85 will be summarized by protection against colonization (colonized/non-colonized) and by treatment group and by timepoint. Comparison between colonized subjects and non-colonized subjects will be made using separate two-sample t-tests by treatment group and by timepoint.

The number and proportion of subjects with $\geq 50\%$ killing titer (or equivalent) at Day 113 compared to baseline and Day 29 will be summarized by treatment group and by timepoint. The 95% CI will be provided by using Agresti-Coull method. A McNemar test will be used to compare proportions between timepoints in each treatment groups (Day 113 vs baseline; Day 113 vs Day 29).

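### Substudy coloniser/non-coloniser antibody t-tests that combine randomised arms carry no arm term, so they can signal a serum correlate of protection that exists within no arm

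*SAP*

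**What the plan says.** The serum objective in SAP 2.3.2 asks whether antibody at Day 29 or Day 85 "is relational to protection against colonization by treatment group and overall (BPZE1, BPZE1 + Boostrix, Boostrix"). The matching endpoint in SAP 3.2.3.2 is "compared by protection against colonization (Colonizers/Non-colonizers) (tested independently by treatment group and overall"). Its group list has the three randomised arms and a fourth group that pools BPZE1 with BPZE1 + Boostrix. Protocol Section 2.2 has the same objective and endpoint.

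The serum method is in SAP 8.4.3. It summarises "BPZE1, BPZE1+Boostrix, BPZE1 and BPZE1+Boostrix, Boostrix control induction of serum immunity (IgA, IgG) at Days 29 and 85" by colonisation status and then states: "Comparison between colonized subjects and non-colonized subjects will be made using separate two-sample t-tests by treatment group and by timepoint". The pooled pair is among the groups. The all-arms comparison is not.

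For mucosal S-IgA, SAP 8.4.2 gives the same kind of test for the same four groups: "Separate two-sample t-tests will be used to compare the natural log-transformed GMRs at Days 29 and 85 between Colonizers and Non-colonizers by treatment group". No S-IgA analysis in either document combines all three arms.

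Neither section gives an arm covariate or stratum for these comparisons. Yet SAP 8.4.2 uses ANCOVA a few lines later, to compare substudy participants with non-participants. SAP Section 4 sets the level: "All statistical tests will be 2 sided at 0.05 significance level". On size, SAP 3.1 says: "Up to 120 enrolled subjects may participate in the substudy".

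**The concern.** The question is whether a child with more antibody is better protected. In a group that mixes arms, randomised arm can drive both variables, and the documents expect it to:

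- **Colonisation.** SAP 2.3.3 sets out to show that prior BPZE1 substantially reduces it. Protocol 1.1 reports such protection in adults after BPZE1 but not after Boostrix.
- **Serum IgG.** Protocol 6.4 notes that BPZE1 lacks the purified PT, FHA and PRN levels found in Boostrix, so IgG to these antigens may well be higher in the two Boostrix-containing arms.

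Colonised children would then come disproportionately from the Boostrix-only arm, and an unadjusted overall t-test would largely compare arms. A serum marker with no link to protection inside any arm could look protective, or IgG could look harmful. In the pooled BPZE1 pair, an antibody gap between the two arms also adds variance and hides a real relation.

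The single-arm tests avoid this but are weak. With 40 children in an arm and 10–50% colonised, power for a true 0.5-SD relation is only about 15–33%. The mixed-arm tests are therefore likely to carry any statement about a correlate.

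**Working it through.** **The plan's own figures.** The documents state no power or error rate for this comparison. The nearest figures are in SAP Table 4-2, whose SDs set the scale here. With 108 per group and one-sided 0.025, the noncentrality is (mean difference + 0.693) / (SD × √(2/108)). For PT this is 0.459 / (0.8759 × 0.1361) = 3.85. The noncentral t gives 97.0% for PT, 100% for FHA and 88.2% for PRN, all as stated. On these SDs, a 1-SD gap is exp(0.8759) = 2.4-fold for PT and exp(1.4363) = 4.2-fold for PRN.

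**Inputs for the check.** From the SAP: a cap of 120 children, the two-sample t-test on ln antibody, and two-sided 0.05. Assumed: even opt-in (40 per arm), the colonisation rates, the antibody gap d in SD units, and equal SDs. Rates are in the order BPZE1 / BPZE1 + Boostrix / Boostrix. Antibody is unrelated to colonisation inside every arm.

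**Formula.** Let s be the share of children from the higher-antibody arms, among colonised (s₁, n₁ children) and non-colonised (s₀, n₀ children).

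- Spurious mean difference = d × |s₀ − s₁|.
- Variance within each colonisation group = 1 + d² × s(1 − s), pooled over the two groups.
- SE = √(pooled variance) × √(1/n₁ + 1/n₀).
- Rejection rate ≈ Φ(difference/SE − 1.96), plus a negligible opposite tail.

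**Worked case.** Colonisation is 30/30/80% and serum IgA is 1 SD higher in both BPZE1 arms. Colonised: 12 + 12 + 32 = 56, so s₁ = 24/56 = 0.429. Non-colonised: 28 + 28 + 8 = 64, so s₀ = 56/64 = 0.875. The difference is 0.446 SD. The variances are 1.245 and 1.109, pooled 1.172. SE = 1.083 × 0.183 = 0.198. The ratio is 2.25, so rejection ≈ Φ(0.29) = 61%.

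| Comparison | Colonisation | Gap | Spurious difference | Approximate rejection | Simulated |
|---|---|---|---|---|---|
| Overall, IgA higher in BPZE1 arms | 30/30/80% | 1 SD | 0.446 | 61% | 61–62% |
| Same | 30/30/60% | 1 SD | 0.278 | 27% | 27–28% |
| Overall, IgG higher in Boostrix arms | 30/30/80% | 1 SD | 0.223 | 20% | 18–20% |
| Same | 30/30/80% | 2 SD | 0.446 | 44% | 43–44% |
| Same | 30/30/60% | 1 SD | 0.139 | 10% | 9–10% |
| Same | 30/30/60% | 2 SD | 0.278 | 19% | 17–19% |
| Pooled BPZE1 pair | 20/40% | 1 SD | 0.238 | 14% | 13–15% |
| Same | 20/40% | 2 SD | 0.476 | 29% | 28–29% |

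The simulated column spans repeat runs of 3,000 to 5,000 substudies each. In the IgG rows nearly every rejection has the higher IgG in colonised children. With arm in the model, rejection is 4–6% in every row. With equal colonisation in all arms (30/30/30%), or in both arms of the pair, the plain t-test also stays at about 4–6%, whatever the gap.

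Other assumptions move the size. At SD 0.8759, with the BPZE1 arms 2-fold higher, the overall test rejects 39% of the time at 10/10/50% colonisation and 13% at 20/20/40%.

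**Power in the pooled pair.** Take 30% colonised in both arms (24 of 80), a true 0.7-SD relation and a 1.5-SD gap between arms. Unadjusted SD = √(1 + 1.5² × 0.25) = 1.25, so SE = 1.25 × √(1/24 + 1/56) = 0.305 and the ratio is 2.30. With arm in the model, SE = 0.244 and the ratio is 2.87. Simulated power is about 61% against 79%.

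**The case against.** The strongest objection is that SAP 2.3.2 asks about association both by arm and overall. In the scenarios above a marginal association does exist, so rejecting equal means is correct for that question. If vaccine-induced antibody mediates protection, arm adjustment also removes relevant between-arm signal. This stands as a reason to keep the unadjusted comparison in view, but not to base a correlate statement on it. The mixed test cannot tell mediation from antibody and protection merely sharing an arm, and it can make IgG look harmful.

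Four further points stand and limit the concern:

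- The all-arms test appears in the serum objective and endpoint but not in the SAP 8.4.3 method. That it would be a plain t-test is inferred by joining the sections.
- The documents do not say that serum IgA is higher after BPZE1 than after Boostrix. Protocol 1.1 contrasts the two vaccines for mucosal S-IgA only, and the serum IgA objectives against Boostrix are non-inferiority. The IgG case is better supported.
- S-IgA has no overall test. Its only mixed group is two arms given the same BPZE1 dose, and Boostrix did not induce S-IgA in adults, so little inflation is expected there.
- The endpoints are exploratory, in an opt-in substudy whose possible bias Protocol 5.1 acknowledges. No success criterion for the main study or sample size rests on these comparisons.

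A reader might infer that the planned tests as a whole reject because arms differ and not because antibody relates to protection. The documents do not support that. The single-arm tests are planned and unaffected, inflation needs arms to differ in both antibody and colonisation, and a mixed-arm rejection does not show that antibody is unrelated.

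**Conclusion.** The concern holds for the serum comparisons that combine arms. Under the plan's premises an unadjusted overall test would reject well above 5% with no within-arm relation: about 10–44% for IgG 1–2 SD higher in the Boostrix arms, and about 27–61% if serum IgA is 1 SD higher in the BPZE1 arms. The pooled BPZE1 pair is inflated (about 14–28% at an assumed 20% against 40%) only if its two arms colonise differently. At equal colonisation, a serum IgG gap between them still costs power.

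The absence of an arm term, and the mismatch between SAP 3.2.3.2 and 8.4.3 over the overall test, can be read directly from the text. The sizes rest on assumed colonisation rates, antibody gaps, equal SDs and even opt-in, none of which the documents give. The change is worth making before the analysis, at exploratory level.

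**What to change.** In SAP 8.4.3, and for consistency in 8.4.2:

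- For every comparison that combines arms, fit a linear model of ln antibody on colonisation status plus randomised arm, or stratify by arm. Base any correlate statement on that estimate.
- Report unadjusted mixed-arm comparisons as descriptive only.
- Keep the two-sample t-test within single arms.
- State in 8.4.3 whether the overall serum comparison named in 2.3.2 and 3.2.3.2 will be run, and make the sections agree.

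The cost is a few lines of SAP text and one covariate, with a method the SAP already uses. No new data are needed.

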3.2.3.3. Colonization (Optional Substudy Only)

- Subjects with colonization at each of Days 92 and 99 by treatment group. Expressed as absolute proportion and percent reduction relative to control.

3.2.3.4. Other Exploratory Endpoints

- Cellular-mediated response at baseline and Day 8 (safety lead-in cohort) and Days 85 and 113 (subset of substudy subjects).
- Immunologic response measurement by treatment group.

3.3.Treatments

Subjects in Treatment Group A (N ~120) will receive an intranasal application of 10^9 CFU BPZE1, with approximately 0.4 mL per nostril (0.8 mL total volume delivered); and an IM injection of 0.5 mL placebo (sterile normal saline for injection, or similar sponsor-approved substitute) to the deltoid region on Day 1.

Subjects in Treatment Group B (N ~120) will receive an intranasal application of 10^9 CFU BPZE1, with approximately 0.4 mL per nostril (0.8 mL total volume delivered); and an IM injection of 0.5 mL Boostrix (aP vaccine, manufactured by GlaxoSmithKline) to the deltoid region on Day 1.

Subjects in Treatment Group C (N ~120) will receive an intranasal application of lyophilized buffer reconstituted in sterile water, with approximately 0.4 mL per nostril (0.8 mL total volume delivered); and an IM injection of 0.5 mL Boostrix (aP vaccine, manufactured by GlaxoSmithKline) to the deltoid region on Day 1.

Intranasal application of BPZE1 or placebo should precede IM injection of Boostrix or placebo by at least 10 minutes. For the safety lead-in cohort, a minimum of 30 minutes must occur between intranasal and IM vaccinations on Day 1.

All subjects participating in the optional substudy will receive a second intranasal application of 10^9 CFU BPZE1, with approximately 0.4 mL per nostril (0.8 mL total volume delivered) on Day 85.

All subjects will be monitored for study vaccination-related events for at least 30 minutes following the last vaccination (e.g., 30 minutes following IM vaccination).

4. General Statistical Considerations

Continuous variables will be summarized using the mean, standard deviation (SD), median, first quartile, third quartile, interquartile range (IQR), minimum value, and maximum value.

Categorical variables will be summarized using frequency counts and percentages, as well as a 2-sided 95% confidence interval (CI) for proportions computed using the Agresti-Coull method when appropriate.

Baseline is defined as the last non-missing value before the vaccination on Day 1.

For summary precision, mean and median will have one more decimal place than the reported value, SD will have two more decimal places than the reported value, minimum and maximum will have the same decimal place as the reported value. Percentages and 95% CIs will have one decimal place.

For immunogenicity analysis, it is assumed that the natural log of the data is normally distributed for the GMT/GMC/GMR, and GMFR.

GMT/GMC/GMR will be calculated as anti-logarithm of \sum (log-transformed titer/number of subjects with titer information). The 95% CI for GMT/GMC/GMR will be calculated as the anti-log transformation of upper and lower limits for a 2-sided 95% CI of the mean of the log-transformed values based on normal approximation.

For any antibody titer, if the result is reported as lower than the minimal limit of assay detection, a value equal to half of the minimal limit of assay detection will be imputed in the calculation. The minimal limit of assay detection for each of the antibody titers will be established following assay validation and prior to database lock.

GMFR will be calculated as anti-logarithm of \sum [log-transformed titer ratio of (Yi/Bi)/number of subjects with titer information], where Yi is the post-dose titer and Bi is the baseline titer for subject i. The same data summaries will be provided as GMT/GMC/GMR.

The mucosal and serum immunogenicity descriptive summaries (GMT/GMC/GMR and/or GMFR) will be provided by treatment group and by timepoint and across timepoints if applicable (all subjects), including a separate analysis after Day 85 for the open-label substudy. Analyses will include the GMT/GMC/GMR with 95% CIs and GMFRs with 95% CIs.

For seroconversion of mucosal S-IgA and serum IgA and IgG against WCE, PT, FHA, PRN, and any additional anti-pertussis antibodies identified during assay development, descriptive summaries including seroconversion rates and the 95% CIs will be provided by treatment group and by timepoint. Mucosal S-IgA will be normalized as [specific S-IgA]/[Total S-IgA (mg/mL)] and it will also be summarized using same method.

Immunogenicity endpoints (seroconversion, GMT/GMC/GMR, and GMFR) will be summarized by baseline PRN negative and PRN positive status, by quantiles of each anti-pertussis antibody (WCE, PT, FHA, PRN, and any additional anti-pertussis antibodies) and by antibody type (eg, S-IgA, IgA, and IgG separately), by the 2 age groups (6 to 10 years and 11 to 17 years, inclusive) and across age groups. An additional age group of 10 to 17 years will be added for some analyses to be able to support a rationale for immunobridging to adults. A forest plot will be generated for subgroups.

The substudy analysis will assess immunogenicity endpoints at baseline and Days 85 and 113 (independently for substudy subjects) and relative to colonization status (colonized/non colonized) at either or both Day 92 and/or 99 following re-vaccination/attenuated challenge at Day 85.

All statistical tests will be 2 sided at 0.05 significance level.

If a substantial number of subjects receive a COVID-19 vaccine that is under an emergency use authorization only, then safety analysis may also assess any AEs that may be confounded by such concomitant vaccine administration during the study.

All data collected will be listed in data listings.

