7.4.1 Analyses of Primary Endpoints

7.4.1.1 Analyses of Primary Immunogenicity Endpoints

For mucosal S-IgA against WCE at Day 29, the two-sided 95% CI for change from baseline in GMFR will be calculated. A superiority hypothesis will be tested to demonstrate BPZE1 can adequately induce mucosal S-IgA against WCE at Day 29 by GMFR.

The formal superiority hypothesis is:

$$H_0: GMFR \leq 1 \text{ vs. } H_A: GMFR > 1$$

The GMFR is defined as the ratio of GMT at Day 29 and GMT at baseline, i.e.,

$$GMFR = \left(\frac{\mu_{D29}}{\mu_{BL}} \right), \text{ with } \mu_{D29} \text{ and } \mu_{BL} \text{ being the GMTs at Day 29 and baseline, respectively.}$$

After natural logarithmic transformation, $\ln(GMFR) = \ln(\mu_{D29}) - \ln(\mu_{BL})$. Therefore, the hypothesis can be expressed in the natural log scale as:

$$H_0: \ln(\mu_{D29}) - \ln(\mu_{BL}) \leq 0 \text{ vs. } H_A: \ln(\mu_{D29}) - \ln(\mu_{BL}) > 0$$

After natural logarithmic transformation, a paired t-test will be used to test the difference of mucosal S-IgA against WCE at Day 29 compared with baseline. The superiority objective will be demonstrated if the lower limit of the 95% CI for the difference of mucosal S-IgA against WCE at Day 29 compared to baseline on the natural log scale is greater than 0 within the treatment group. The superiority hypothesis will be tested in treatment groups BPZE1 and BPZE1 + Boostrix separately.

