4.1.1. Sample Size for Primary Immunogenicity Endpoints

The sample size is based on calculations to achieve adequate response on Day 29 over baseline of mucosal S-IgA for WCE assay in the BPZE1 and BPZE1 + Boostrix groups. Assuming the GMT follows a log-normal distribution, by applying a natural logarithmic transformation of the GMT, a paired t-test will be used to test the difference of mucosal S-IgA against WCE at Day 29 compared with baseline (equivalent to natural logarithmic transformation of the GMFR). With an effective sample size of N=108 subjects per group, the study provides 95% power for detecting an effect size of 0.35 for each of the two primary comparisons with a two-sided significance level of 0.05. By multiplying the power for each of the two comparisons, the study provides an overall power of 90% (=95%*95%) for testing both primary comparisons (BPZE1, BPZE1+Boostrix). Factoring in an estimated 10% drop-out rate, each treatment group would include approximately 120 subjects for a total of approximately 240 subjects in the study for the primary analysis. An additional 120 subjects are randomized to the Boostrix group for the assessment of non-interference resulting in a total of approximately 360 subjects in the study.

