$$H_0: \ln(\mu_{D29}) - \ln(\mu_{BL}) \leq 0 \text{ vs. } H_A: \ln(\mu_{D29}) - \ln(\mu_{BL}) > 0$$

After natural logarithmic transformation, a paired *t*-test will be used to test the difference of mucosal S-IgA against WCE at Day 29 compared with baseline. The superiority objective will be demonstrated if the lower limit of the 95% CI for the difference of mucosal S-IgA against WCE at Day 29 compared to baseline on the natural log scale is greater than 0. The superiority hypothesis will be tested in treatment groups BPZE1 and BPZE1 + Boostrix separately. These 2 primary comparisons will be tested at a one-sided significance level of 0.025. The study is considered a success if both primary comparisons meet statistical significance.

Sensitivity analysis for primary endpoints will be performed based on the Immunogenicity Analysis Set.

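### The normal-approximation intervals in SAP Section 4 for GMT and GMFR run slightly narrow: about 94 to 95% coverage in the cells that can be sized, less only in very small ones

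*SAP*

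**What the plan says.** SAP Section 4 (General Statistical Considerations) takes the interval for GMT, GMC and GMR from "a 2-sided 95% CI of the mean of the log-transformed values based on normal approximation". For GMFR it adds: "The same data summaries will be provided as GMT/GMC/GMR". It names no t quantile and no degrees of freedom. The same section states the model: "it is assumed that the natural log of the data is normally distributed for the GMT/GMC/GMR, and GMFR".

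SAP Section 4 then repeats these summaries by baseline PRN status, baseline antibody quantile and age group, with a forest plot. SAP Sections 8.3.1 and 8.3.2 add time since last aP vaccination and other baseline demographics. SAP Sections 8.4.2 and 8.4.3 summarise the substudy by colonizer or non-colonizer status within arm.

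The formal analyses use a different reference distribution. SAP Section 8.1 tests the log ratio to baseline by paired t-test, as does Protocol Section 7.4.1.1: "After natural logarithmic transformation, a paired t-test will be used to test the difference of mucosal S-IgA against WCE at Day 29". Success is then read from an interval: "The superiority objective will be demonstrated if the lower limit of the 95% CI for the difference of mucosal S-IgA against WCE". Section 8.1 does not name the quantile for that interval. SAP Section 1 makes the SAP govern where the two documents differ.

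**The concern.** If the logs are normal and the SD is estimated from the same children, the exact 95% interval for the log mean uses the t quantile with n-1 degrees of freedom. The normal quantile is smaller, so the interval is too narrow, and the error grows as the cell shrinks. Followed as written, the rule gives descriptive tables and forest plots that overstate precision, most of all in the smallest cells.

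It also leaves one quantity with two possible 95% intervals. A programmer working from Section 4 would use z for the GMFR summary; one working from Section 8 would use the interval that goes with the paired t-test. A pre-specified plan should lead both to the same limits.

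**Working it through.** **Inputs from the documents.**
- 120 randomised per arm and 108 effective after 10% dropout (SAP Section 4.1.1).
- At most 120 children in the substudy (SAP Section 3.1).
- Normal logs (SAP Section 4).
- Primary level: "These 2 primary comparisons will be tested at a one-sided significance level of 0.025" (SAP Section 8.1).

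**Assumptions of this review.**
- Even opt-in at the cap: 120/3 = 40 per substudy arm.
- Quartiles, since the number of quantiles is not stated: 108/4 = 27.
- An even two-way split of an arm: 108/2 = 54.
- A quartile crossed with two equal age groups: 27/2, about 13.
- Any smaller cell is illustrative.

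**The plan's own figure.** SAP Section 4.1.1 states: "With an effective sample size of N=108 subjects per group, the study provides 95% power for detecting an effect size of 0.35". For the paired t-test the noncentrality is 0.35 × √108 = 3.637 with 107 degrees of freedom. Power is 0.94996, and 0.94996² = 0.902 for both arms. The stated 95% and 90% are reproduced.

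**Coverage of the literal rule.** For mean ± 1.96 × SD/√n with normal logs, coverage is P(|t with n-1 df| < 1.96). The last column is the t quantile divided by 1.96, that is, how much wider the exact log-scale interval is.

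| Cell | n | Coverage | t/z width |
|---|---|---|---|
| Full arm | 108 | 94.7% | 1.011 |
| Half arm (assumed) | 54 | 94.5% | 1.023 |
| Substudy arm (assumed) | 40 | 94.3% | 1.032 |
| Quartile of an arm (assumed) | 27 | 93.9% | 1.049 |
| Illustrative | 20 | 93.5% | 1.068 |
| Illustrative | 15 | 93.0% | 1.094 |
| Quartile by age group (assumed) | 13 | 92.6% | 1.112 |
| Illustrative, 8 of 40 | 8 | 90.9% | 1.207 |
| Illustrative, 3 of 40 | 3 | 81.1% | 2.195 |

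A simulation of 100,000 runs per size agreed: 81.3% at n=3, 93.1% at 15, 93.9% at 27, 94.3% at 40 and 94.8% at 108.

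**Primary comparison at n=108.** If z were used for the lower limit, the one-sided error would be 2.63% instead of 2.50%, and power at effect size 0.35 would be 95.2% instead of 95.0%. The two rules give different answers only when the t statistic lies between 1.960 and 1.982. That has probability 0.13% at the null boundary and 0.23% at effect size 0.35.

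**The case against.** The strongest reply has three parts.

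1. **Wording.** Section 4 gives no 1.96. It could loosely mean normal theory on the log scale with a t quantile. That is possible, but z is the literal reading, and if t was intended the correction only records it.

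2. **Much of the output is already tied to t.** SAP Sections 8.3.1 and 8.3.2 attach intervals to paired t-tests against baseline by arm and visit, and SAP Sections 8.4.2 and 8.4.3 do so for Day 113. Colonizer comparisons use two-sample t-tests, and the key secondary pertussis-antigen comparisons use ANCOVA. This stands. What remains exposed is descriptive: per-group GMTs and GMFRs, subgroup plots, and colonizer and non-colonizer summaries. No decision rule hangs on them.

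3. **Cell sizes.** A reader might infer that the trial's 95% intervals generally cover only 81 to 93%. The documents do not support that. Those figures need about 3 to 19 children, and no subgroup, quantile or colonizer count is stated. The quantile-by-age cross is not clearly specified, and repeated visits do not divide the children into smaller cells. The one documented group of about 15 is a lead-in arm (45 over three arms). Its Day 8 cellular data get an interval for the median (Protocol Section 7.4.5), so this rule does not apply to them.

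A reader might also infer that the primary GMFR interval conflicts with the primary test. Section 8.1 names the paired t-test and, in the next sentence, the interval for the same difference, so the paired-t interval is the natural reading. Even with z, the effect is 1.1% in width.

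**Conclusion.** The point holds as a minor correction. The rule in SAP Section 4, taken as written, under-covers whenever the SD is estimated. Coverage is 94.7% for a full arm and 93.9 to 94.5% for cells of 27 to 54, which rest on the assumptions of quartiles, even opt-in and even splits. It falls to about 93% at 13 to 15, 91% at 8 and 81% at 3. Colonizer cells in the BPZE1 arms could be that small if prior vaccination reduces colonization as hypothesised, but this is an assumption. All coverage figures take the SAP's normal-log assumption as true. Sample size, power and the primary and key secondary conclusions are not materially affected.

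**What to change.** In SAP Section 4, replace the reference to a normal approximation with Student's t distribution with n-1 degrees of freedom, and say that this applies to GMT, GMC, GMR and GMFR. For certainty, add to SAP Section 8.1 that the primary interval is the paired-t interval.

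The cost is a phrase and a sentence. Exact intervals are wider on the log scale by 1.1% at n=108, 4.9% at n=27 and 9.4% at n=15; at n=3 they more than double. In return, tables and forest plots have nominal coverage under the SAP's own assumption and agree with the t-tests in Section 8.
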